5.1 Potential benefit for elderly patients with first AML diagnosis

In elderly AML patients with standard cytogenetic risk, treatment with intensive chemotherapy results in median overall survival of up to 12 months, whereas in the adverse cytogenetic category median survival is only 2-3 months (Lagadinou, 2010). The median age at presentation for patients with AML is about 65 years and in this age group, AML is associated with a poor prognosis. Therefore, AML in the elderly represents a major unmet medical need.

Asparaginase has been used in some treatment protocols for AML in children. Capizzi (1988) has reported a significant benefit of Asparaginase in AML. However, its use remains hampered due to its toxicity. The use of L-asparaginase has a potential interest in AML, in light of the fact that AML blasts display a low level of ASNS (see section 3.2).

GRASPA has been proposed as a new approach to maintain the activity of L-asparaginase while improving its safety profile. Recent experience of GRASPA in ALL with an elderly population >55 years, demonstrated a

tolerable safety profile. This study showed that GRASPA favorable safety profile of both doses 100 and 150 IU/Kg (GRASPALL 2007-04). A recent PK/PD re-analysis of all completed studies with GRASPA demonstrated that age has no impact on the PK of different dosing levels; and therefore, a dosing schedule of 150 IU/Kg every 2 weeks is proposed as a standard dose for all age groups.

The objective of the development of GRASPA in AML is evaluate the overall survival benefit and the both progression free survival and event free survival and patient quality of life, as well as assess the impact on ASNS profile of myeloblasts as an exploratory objective.

5.2 Potential risks for the patients

The Potential toxicity of GRASPA results from 2 main mechanisms: (1) toxicity related to L-asparaginase, (2) toxicity associated with erythrocyte.

5.2.1 Risk associated with L-asparaginase

When L-asparaginase (free formulation as *E. Coli* L-asparaginase) is given, major effects observed include mainly hypersensitivity reactions related to the direct immunogenicity of the compound and pancreatic, hepatic or coagulation disturbances, probably related, in part, to asparagine depletion (Kurtzberg 2007).

These toxicities are treatment-limiting especially in frail populations such as elderly patients.

The encapsulation of L-asparaginase (GRASPA) eliminates the direct somatic contact with the Lasparaginase, and it is hypothesized that this provides the potential to reduce toxicity associated with the parent L-asparaginase and prolong the activity of the enzyme. On the basis of the pharmacological effects of L-asparaginase, GRASPA is expected to have a therapeutic benefit in AML.

In study GRASPALL 2009-06, the incidence of allergic reactions was significantly lower in both GRASPA arms in the non-allergic (7.7%) and allergic patients (11.5%), as opposed to a rate of 57.1% in patients treated with native-asparaginase. There were no withdrawals due to hypersensitivity reactions, either in the allergic or non-allergic patient subsets. The most common drug-related events with GRASPA were hypofibrinogenemia (26.9%), asymptomatic pancreatitis (26.9%), elevated transaminases (19.2%), hypoalbuminemia (15.4%), and decreased anti-thrombin III (11.5%). By contrast, most of these events took place at greater incidence (64.3%, 53.6%, 21.4%, 32.1%, and 71.4% for hypofibrinogenemia, asymptomatic pancreatitis, elevated transaminases, hypoalbuminemia, and decreased anti-thrombin III, respectively). These results indicate that GRASPA is anticipated to have a favorable safety profile in patients with AML unfit to receive intensive chemotherapy.

5.2.2 Risk associated with erythrocytes administration

Blood transfusion can cause adverse effects, either related to the patient's particular condition, or to blood product, blood donor and blood transfusion procedure. These adverse events are well known (American Association of Blood Banks 1996; AFSSAPS 2003).

The quantity of encapsulating erythrocytes administered as GRASPA are reduced compared to those used in usual blood transfusion practices. The volume of erythrocytes (leukocyte-depleted RBC in a SAG-mannitol suspension) injected per unit of RBC (280 ml) corresponds to approximately 4.6 ml/kg of an 18 g/dL suspension (HCT/PCV 60%). Comparatively, an administration of GRASPA at a dose of 100 IU/kg and 150 IU/kg corresponds to 1.8 mL/kg, respectively 2.7 mL/kg of a 13 g/dL hemoglobin suspension (HCT/PCV 50%).

Safety data from 189 patients treated with GRASPA as of March 2015, all transfusion reactions occurred in 5.8% of the patients, of which 1.1% were serious. None of the AE was related to GRASPA.

Further, clinical studies with GRASPA have a clear guidance regarding monitoring of the patients during transfusions. In the event of transfusion reactions, transfusion must be stopped immediately and the necessary symptomatic treatments administered according to standard of care.

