4.3.2 Secondary endpoints

- Percentage of patients with Complete remission (CR), Complete remission with incomplete recovery (neutrophil or platelet regeneration, CRi), Partial remission (PR)
- Progression-free survival (PFS) defined as the time elapsed between randomization and resistant disease or relapse or death from any cause
- Relapse Free Survival defined only for patients who achieved CR or CRi as the time elapsed between date of CR/CRi and date of disease relapse or death from any cause
- Percentage of patients who need transfusions (red blood cells and/or platelets), number of transfusions by patient
- Patient quality of life evaluated using the EORTC QLQ-C30 version 3 scale
- Number of hospitalizations (except scheduled protocol visit) required during the study
- Safety of GRASPA in combination with low-dose cytarabine, with specific attention to :
 - o Grade 3 or 4 of Pancreatic toxicity
 - o Grade 3 or 4 of hepatic toxicity, allergic reaction or coagulation event
 - o Grade 3 or 4 of hypoproteinemia or hyperglycemia/diabetes
 - All other non-hematologic Grade 4 toxicities

(*NB* grading reference used: NCI CTCAE version 4.0)

- Pharmacokinetic and pharmacodynamic parameters:
 - o Plasma concentrations of asparagine, aspartate, glutamine, glutamate
 - Whole Blood L-asparaginase activity
- Immunogenicity by measuring titer of anti-L-asparaginase antibodies
- Biomarker cytogenetic testing (optional)
- Measurement of the following parameters on harvested bone marrow tumor cells (optional):
 - Asparagine synthetase protein expression
 - Asparagine synthetase mRNA expression
 - In vitro sensitivity to L-asparaginase

(See also section 8.8 for details)

Table 3 hereafter provides the definitions of response criteria in AML.

Category	Definition
Complete remission (CR)*	Bone marrow blasts < 5%; absence of blasts with Auer rods; absence of extramedullary disease; absolute neutrophil count > $1.0 \times 10^{9}/L$ (1000/µL); platelet count > $100 \times 10^{9}/L$ (100 000/µL); red blood cell transfusion independence
CR with incomplete recovery (CRi)	All CR criteria except for residual neutropenia ($< 1.0 \times 10^{9}/L [1000/\mu L]$) or thrombocytopenia ($< 100 \times 10^{9}/L [100 000/\mu L]$)
Partial remission (PR)	all hematologic criteria of CR; decrease of bone marrow blast percentage to 5% to 25%; and decrease of pre-treatment bone marrow blast percentage by at least 50%

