9.2 Posology

GRASPA is a ready to use suspension designed to be fully injected.

The dose of GRASPA is 100 IU/kg. In this study protocol, patients will receive one infusion of GRASPA on Day 11 of 28-day course of chemotherapy (see section 10.1).

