5.6.2.4. Transfusions

For collection of information regarding transfusions, the following variables will be collected at each visit:

- Transfusions (Yes/No)
If yes,
 - mean number of transfusions
 - mean weekly number of transfusions
 - mean number of units transfused
 - at least 1 transfusion of RBC (Yes/No)

- at least 1 transfusion of platelets (Yes/No)
- at least 1 transfusion of other (Yes/No) and specifications

Any transfusion occurring after a PD will not be taken into account.

The number of transfusions will be grouped by quarter, up to an event (PD/death) and overall, by treatment group, using descriptive statistics. The mean number of transfusions of RBC and/or platelets required during the study, along with a corresponding 95% CI, will be calculated.

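### GRASPA infusions supply donor red cells to arm B only, so RBC transfusion counts are not like-for-like as a measure of disease control

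*Protocol*

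**What the plan says.** Protocol 9.1 describes GRASPA as prepared from leukocyte-depleted packed red cells, and 3.3 says its cells leave the circulation as transfused cells do. On posology, 9.2 states "The dose of GRASPA is 100 IU/kg" and that "patients will receive one infusion of GRASPA on Day 11 of 28-day course of chemotherapy". Only arm B receives it.

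Protocol 5.2.2 gives the red-cell content. A 280 mL unit "corresponds to approximately 4.6 ml/kg of an 18 g/dL suspension (HCT/PCV 60"% haematocrit). GRASPA at 100 and 150 IU/kg "corresponds to 1.8 mL/kg, respectively 2.7 mL/kg of a 13 g/dL hemoglobin suspension", at 50% haematocrit. The text concludes only that the quantity is smaller than in usual transfusion practice.

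Transfusion need is a secondary efficacy endpoint (Protocol 4.3.2, SAP 3.5.1). Protocol 8.8 records transfusions of packed RBC or platelets and does not mention GRASPA. SAP 5.6.2.4 lists number, weekly number and units transfused, then "at least 1 transfusion of RBC (Yes/No"), the same for platelets, and an item for other products. The mean with its 95% CI is specified for RBC and/or platelets together.

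In Protocol Table 3 (section 4.3.2), CR includes "red blood cell transfusion independence". CRi inherits this, and PR requires the haematologic criteria of CR. SAP Table 4 words the criterion as independence of transfusions in general. Neither gives a time window.

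**The concern.** One arm receives a scheduled supply of red cells as part of its study drug, and the other does not. If the infusions stay outside the transfusion count, arm B can need fewer packed-RBC transfusions simply because some of its need has been met by the carrier. If they were counted, every dosed arm B patient would be transfused in every course, and the comparison would tilt the other way. The plan states neither rule.

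The SAP introduction judges activity on the size of effect across several endpoints together, not on OS alone. A lower RBC requirement on GRASPA could then be taken as supporting evidence of anti-leukaemic activity when part of it is carrier cells. The item for other transfused products adds a practical risk, because sites could differ in whether they enter an infusion there.

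**Working it through.** **Inputs (Protocol 5.2.2 and 9.2).** Red-cell unit: 280 mL, 4.6 mL/kg, 18 g/dL, haematocrit 60%. GRASPA at 100 IU/kg: 1.8 mL/kg, 13 g/dL, haematocrit 50%. One infusion per 28-day course.

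**Checking the protocol's own figures.**
- 1.8 × 150/100 = 2.7 mL/kg, as stated for 150 IU/kg.
- 280/4.6 = 60.9 kg, so the per-kg figure for a unit refers to a patient of about 61 kg.

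**Haemoglobin per kg.**
- GRASPA: 1.8 mL/kg × 0.13 g/mL = 0.234 g/kg.
- Unit: 4.6 mL/kg × 0.18 g/mL = 0.828 g/kg.
- Ratio: 0.234/0.828 = 0.283. Rounding in the four inputs allows 0.25 to 0.31.
- By red-cell volume instead: (1.8 × 0.50)/(4.6 × 0.60) = 0.90/2.76 = 0.33.

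**Dependence on weight.** GRASPA is dosed per kg, whereas a unit is fixed at 280 × 0.18 = 50.4 g. The unit equivalent of one infusion is therefore 1.8 × kg × 0.13 / 50.4.

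| Weight (kg) | Hb per infusion (g) | Unit equivalents |
|---|---|---|
| 50 | 11.70 | 0.23 |
| 60.9 | 14.24 | 0.28 |
| 70 | 16.38 | 0.33 |
| 80 | 18.72 | 0.37 |
| 90 | 21.06 | 0.42 |

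**Accumulation at about 61 kg.** 0.57 unit after 2 infusions, 1.13 after 4, 1.70 after 6. Transfusions after progression are excluded (SAP 5.6.2.4), and the planned median PFS on GRASPA is 3.5 months (SAP 5.1), which spans about four infusions. RBC need accumulates over the same courses, so the share of need is the relevant measure.

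**Share of need.** The documents give no RBC need. The values below are assumptions, using 0.283 unit per 28 days.

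| Assumed need (units per 28 days) | Share met by the carrier |
|---|---|
| 0.5 | 57% |
| 1 | 28% |
| 2 | 14% |
| 4 | 7% |
| 8 | 4% |

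**Offset from PK sampling.** Under the amended schedule (Protocol Table 5, Appendix 3), arm B gives about 8 × (4 + 2 × 2) + 2 = 66 mL of blood in each of two courses. At an assumed 7 to 10 g/dL this is 4.6 to 6.6 g haemoglobin, leaving a net 0.15 to 0.19 unit in those courses at about 61 kg.

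**Schedule conflict.** Protocol 8.5.3 refers to GRASPA every 14 days when cytarabine is stopped, against once per 28-day course in 9.2. On the former the supply would be about 0.57 unit per 28 days. The two passages must be reconciled.

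**The case against.** The strongest reply is that the comparison remains randomised. The endpoint is transfusion need, and fewer packed-RBC transfusions on the GRASPA regimen is a real effect of that regimen. This stands: only the attribution to disease control is affected. A reader might infer that the arms cannot be compared at all, or that any difference seen would be an artefact. The documents support neither inference.

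The plan also settles some of this implicitly. Protocol 8.8 counts packed RBC and platelets, and 9.5 treats a blood transfusion as an event distinct from a GRASPA infusion. Infusions are therefore most naturally read as uncounted, although 9.6 loosely calls the infusion a transfusion. The SAP already reports RBC and platelets separately as Yes/No items, so it would be wrong to say that they are pooled throughout. The item explicitly pooled is the mean with its CI.

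A reader might also infer that CR rates are inflated. CR additionally requires the blast, Auer-rod, extramedullary, neutrophil and platelet criteria, and carrier red cells help with none of these. Only a patient who meets all the rest and is tipped into RBC independence would be affected, and the documents do not let us estimate how many there are.

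Finally, the stakes are modest. The transfusion section specifies descriptive summaries with CIs and no between-arm test, and the decision on whether the drug is promising rests on the OS hazard ratio (Protocol 15.3.1, SAP 5.1). That lowers the priority. It does not remove the point, since the SAP introduction also draws on the other endpoints.

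**Conclusion.** The point holds as a limited one. At the trial dose each infusion supplies about 0.28 of a red-cell unit at about 61 kg, in arm B only, and nothing in the plan allows for it. With infusions uncounted, the direction favours GRASPA. The size is unknown: small in heavily transfused patients, and potentially material in those near transfusion independence.

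This rests on three assumptions: the protocol's stated concentrations and volumes, the full bag being given, and haemoglobin content being a fair measure of red-cell supply. A flat 0.28 for every patient is not supported, because the figure moves from 0.23 to 0.42 between 50 and 90 kg. OS, marrow blast criteria and platelet transfusions are untouched by this supply. Any effect on CR, CRi or PR, and through CR/CRi on entry to the RFS set, is possible but not quantified.

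**What to change.** This is a cheap improvement. In SAP 5.6.2.4:

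1. State that GRASPA infusions are not counted as transfusions, including under the item for other products.
2. Report the mean number of transfusions and of units separately for RBC and for platelets, with platelets identified as the comparison free of carrier red cells.
3. Add a sensitivity analysis of RBC units that adds, for each infusion received, its haemoglobin equivalent from the patient's actual weight: 1.8 mL/kg × kg × 0.13 g/mL ÷ 50.4 g per unit.

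Optionally, add a response sensitivity analysis that leaves out the RBC-independence criterion.

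Weight is recorded at visits and on each prescription sheet (Protocol 8.10, 9.6), and administration is documented (9.8), so no new data are needed and treatment does not change. The cost is a few lines of SAP text and one or two extra tables.

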5.3 Benefit / Risk ratio

As of March 2015, a total of 189 patients have been treated with GRASPA in various indications. GRASPA has been developed to reduce L-asparaginase toxicities and, based on accumulated data so far, was shown to have an improved tolerability profile as compared to native L-asparaginase, with an important reduction in allergic reaction as well as reduction of coagulation disorders. As provided earlier, the safety and tolerability of GRASPA has been demonstrated in a Phase III trial in patients with ALL aged between 1-55 years, as well as in a Phase II study in elderly patients with ALL, aged over 55 years.

Therefore, based on the accumulated experience, the potential benefit of GRASPA outweighs the potential risks for assessing its clinical activity and tolerability in elderly patients with AML.

6. Trial design

6.1 Type of trial

This is a multicenter, open label, randomized, controlled phase IIb trial.

6.2 Experimental plan

The primary objective of the trial is to estimate whether GRASPA plus low-dose cytarabine is more promising than low-dose cytarabine alone with respect to OS in subjects 65-85 years old, with newly diagnosed AML unfit for intensive chemotherapy. The study however is not powered explicitly for OS and statistical significance in favor of GRASPA plus low-dose cytarabine is not anticipated. A decision as to whether GRASPA appears to be a promising drug in this indication will be based on the numerical values for the hazard ratio for OS. A hazard ratio of ≤ 0.80 will indicate a 20% numerical reduction in the death rate on average over time in the GRASPA group compared to control.

Efficacy data from this study will be summarized and analyzed on an intention-to-treat (ITT) basis using randomized treatment while safety data for this study will be summarized using treatment received.

The analysis of OS will be performed using a stratified log-rank test (stratification factor PS (0, 1 vs 2)) will be used to compare the two treatment arms.

A secondary analysis will be performed using Cox's proportional hazards regression model, allowing for the effect of treatment and possible prognostic factors. For the main criterion of efficacy the significance level will be 0.05 using a two-sided test. OS will be summarized using Kaplan-Meier methods.

PFS will be analyzed as a secondary criterion of efficacy using the same methods as for OS.

The primary analysis of the primary endpoint and the main secondary endpoints for efficacy will take place once all patients have completed 12 months in the study. A further supportive set of analyses will take place following completion of 24 months in the study for all patients.

There will be no interim analysis for either futility or efficacy.

7. Trial population

This trial will enroll patients corresponding to inclusion criteria AND exclusion criteria hereafter.

7.1 Inclusion criteria

To be eligible, patient must meet all the following criteria:

- Patient \geq 65 years old and \leq 85 years old.
- Newly diagnosed AML or post myelodysplastic syndrome (MDS) diagnosed within 6 months prior to study enrollment
- Unfit for intensive chemotherapy (at risk to suffer treatment related pejorative toxicities /early death), due to the presence of one or more of the following criteria:
 - Dependence in activities of daily living owing to the presence of comorbidities other than those resulting from the deterioration caused by the neoplastic disease.
 - Presence in the patient's medical history of three or more of the following comorbidities, even if they are under control with proper treatment:
 - Congestive heart failure
 - Other chronic cardiovascular diseases
 - Chronic obstructive pulmonary disease
 - Cerebrovascular disease

- Peripheral neuropathy
- Chronic kidney failure
- Hypertension
- Diabetes mellitus
- Systemic vasculitis
- Severe arthritis
- Presence of geriatric syndromes such as fecal or urinary incontinence, spontaneous bone fractures, mild and moderate dementia, or patients who fall repeatedly.

OR

Patient unwilling to receive intensive chemotherapy

- Eligible to receive low-dose cytarabine treatment
- ECOG performance status ≤ 2 .
- Female patients of childbearing potential and males must agree to use adequate contraception (e.g., hormonal or barrier method of birth control; abstinence) for the duration of study treatment and for 6 months after the last dose of cytarabine or 3 months after the last dose of GRASPA (whichever is the longest)
- Negative serum pregnancy test at study entry for female subjects of childbearing potential
- Subscription to social security insurance (if applicable, in accordance with local regulations)
- Ability to understand, and willingness to sign, a written informed consent document and to comply with scheduled visits, treatment plans, laboratory tests, and other study procedures

7.2 Exclusion criteria

- Patients with M3 AML of FAB classification (APL, Acute Promyelocytic Leukemia))
- Patients with AML involving chromosome 16 abnormalities or translocation (8:21) (CBF-AML)
- Patient with Secondary AML subsequent to prior malignant blood disorder such as:
 - Myelodysplastic syndrome diagnosed more than 6 months before study entry
- Myeloproliferative syndrome
- Prior therapy to AML (standard therapy or investigational agents)
- Inadequate organ functions:
 - Uncontrolled or severe cardiovascular disease including myocardial infarction within 6 months of enrollment, New York Heart Association (NYHA) Class III or IV heart failure, uncontrolled angina, clinically significant pericardial disease, or cardiac amyloidosis.
 - Serum creatinine concentration > 2x ULN (Upper Limit of Normal laboratory ranges),
 - $\circ~$ AST or ALT levels > 3.5x ULN or > 5x ULN , if related to AML
 - Total bilirubin levels > 2x ULN
 - \circ INR > 1.5, unless patient under chronic treatment with anticoagulants (in this case, INR should be within expected ranges for the specific condition)
 - Insulin-dependent or uncontrolled diabetes mellitus
- Concurrent malignancies other than AML requiring chemotherapy

- Severe active infection, HIV seropositivity, or known active type B or C viral hepatitis
- Known or suspected hypersensitivity or intolerance to mannitol
- Breastfeeding or lactating women

7.3 Assignment to patient numbers

For confidentiality purpose, complete name of patient enrolled will not be revealed and patient data will be identified with a dedicated patient number in trial records.

Patient number will be composed of 6 digits: first 4 digits corresponding to site number, last 2 digits corresponding to the first number available following that of previous patient included in the trial in the same site. The number will be generated through Interactive Web Response System (IWRS), when minimal data patient are entered.

In countries where this practice is authorized by local regulations, patients may also be identified with initials.

7.4 Assignment to treatment schedule (randomization)

The patients will be randomly and sequentially allocated to either one of the two treatments A or B.

Randomization 1:2 will be performed by an Interactive Web Response System (IWRS, refer to Appendix 2 for randomization process).

After confirmation of randomization, the system will display the treatment arm assigned namely A or B as follows:

A: Low dose cytarabine (see section 10.1)

B: Low dose cytarabine + GRASPA

As poor performance status had been identified as a risk factor that increase probability of early death, and to avoid unbalance between groups, a stratified randomization will be done according to performance status (PS = 0 or 1 vs PS = 2).

